time demands. A comprehensive, individualized plan will be developed to reduce barriers. A motivation assessment questionnaire with established validity and reliability (62, 73, 91) and adapted for a rural community will be used to evaluate preferred types of exercise, social support, and perceptions of barriers to exercise by child and family. Community and environmental barriers to exercise will also be assessed. The Choctaw Nation of Oklahoma offers several social service programs designed to eliminate distress, including academic tutoring, mentoring, organized activities, housing assistance, nutrition classes, and counseling. Many of these services are located near the Wellness Centers. The interviewer will be responsible for linking the family to these services when appropriate and performing follow-up to address new and existing barriers. The goal of this effort is to insure that a decision by the child or family to discontinue the study is due to choice and not due to barriers that can be reasonably addressed.

Baseline pre-training testing: The baseline tests may be combined with the screening visit. Baseline tests will be comprised of measurements of daily physical activity, aerobic fitness, body composition, and insulin resistance. Daily physical activity will be objectively measured with a step-activity monitor worn for 7 days during waking hours. Participants will be asked to maintain their normal lifestyle patterns during this time. A registered dietitian will provide instruction on a healthy eating plan but specific weight loss goals or dietary monitoring will not be part of this study. Insulin resistance and other clinical outcomes will be assessed using fasting blood samples. Participants will report to the research center in the morning following an overnight fast. Body composition and exercise tests will be performed as described below.

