Data analyses: Since group assignments will be balanced for age and sex, the groups are expected to be similar at baseline. Additional comparisons will be performed to identify demographic or other variables on which the groups might differ (e.g., weight loss) that could affect the primary outcomes. Subsequent analyses will adjust for these potentially confounding variables. Regression models, which adjust for modifier (or confounding) variables identified in initial data exploration, will compare between-group differences in the primary outcomes. Since we anticipate that the number of fitness center visits, which is the primary outcome in Aim 1, will follow a Poisson distribution typical of counts, we will explore a multivariable Poisson regression model to analyze that aim. To assess Aim 2, a more conventional regression model will analyze the primary outcome, which is the total time that participants engage in exercise. The effects of exercise training on secondary outcomes will be analyzed similarly, using multiple linear regression. Analysis of Aim 3 will also utilize multivariate modeling to determine which factors, including exercise group assignment, best explain the change in exercise volume and clinical outcomes over the final phase of the study. Residuals generated from regression models will be inspected for normality and data will be log-transformed or subjected to nonparametric testing as appropriate. Aim 4 is a cross-sectional study design so the main effects of physical activity (high versus low), fitness (high versus low) and body size (normal weight versus overweight/obese) on biomarkers of metabolic disease risk will be initially determined using an analysis of variance approach, with Bonferroni tests to make pairwise comparisons between groups. A multivariate modeling approach, similar to that used in Aims 1-3, will be used to identify the best sets of predictor variables for specific biomarkers. A P value <0.05 will be considered statistically significant.

BIBLIOGRAPHY

- 2. Adams SH. Emerging perspectives on essential amino acid metabolism in obesity and the insulinresistant state. *Adv Nutr* 2: 445-456, 2011.

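### Aim 1 covariates are chosen by observed group differences and unspecified data exploration, so the baseline activity and motivation measures already collected are not assured a place in the primary visit-count model.

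*Combined protocol and SAP*

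**What the plan says.** The primary outcome is "the number of fitness center visits, which is the primary outcome in Aim 1", and the model is tentative: "we will explore a multivariable Poisson regression model to analyze that aim". Covariates can enter in two ways, both described in Data analyses.

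- **By group difference.** "Additional comparisons will be performed to identify demographic or other variables on which the groups might differ", with the further condition that the variable could influence the primary outcomes. Then: "Subsequent analyses will adjust for these potentially confounding variables".
- **By exploration.** The regression models will "adjust for modifier (or confounding) variables identified in initial data exploration". No criterion is given for what counts as a modifier, and no variable is named.

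Two relevant measures are taken before training. Under Baseline pre-training testing: "Daily physical activity will be objectively measured with a step-activity monitor worn for 7 days during waking hours". Under Screening: "A motivation assessment questionnaire with established validity and reliability", which "will be used to evaluate preferred types of exercise, social support, and perceptions of barriers to exercise by child and family". Data analyses mentions neither. Group assignment pairs participants on age and sex, but the model is not said to include those factors. The one variable the protocol labels a covariate, exercising with family or friends (Exercise training), is recorded during training and so is not a baseline measure.

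**The concern.** In a randomised comparison, the precision gained by adjusting for a baseline variable depends on how well that variable predicts the outcome. Whether the arms happen to differ on it is a matter of chance. A rule keyed to observed difference therefore selects on the wrong property: a strong predictor that is well balanced has no assured way in. The exploration route might let it in, but only after data have been examined and at the analyst's discretion.

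This bears on the primary comparison. Only 80-90 participants are expected to enter the exercise program (Design), and they choose how often to attend (Exercise training), so visit counts are likely to vary widely between people. If a collected baseline measure explains part of that variation, leaving it out makes the incentive effect less precisely estimated than the data allow.

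**Working it through.** The plan states no power, effect size, visit rate or correlation, so it has no figure of its own to reproduce. Everything below rests on stated assumptions.

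**Inputs from the plan.** 80-90 participants, 1:1 allocation in age- and sex-matched pairs, significance at P<0.05 (sidedness not stated; two-sided assumed).

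**Step 1: formula.** Let R² be the share of outcome variance explained by the baseline covariates. Fixed adjustment multiplies the standard error by √(1−R²). For a comparison with 80% power unadjusted, adjusted power = Φ((1.960+0.842)/√(1−R²) − 1.960), and the equivalent sample size is N/(1−R²).

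| R² (assumed) | SE multiplier | Power | 80 worth | 90 worth |
|---|---|---|---|---|
| 0.05 | 0.975 | 82% | 84 | 95 |
| 0.10 | 0.949 | 84% | 89 | 100 |
| 0.20 | 0.894 | 88% | 100 | 112 |
| 0.30 | 0.837 | 92% | 114 | 129 |

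This is a normal approximation for a continuous outcome, so it was checked on counts.

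**Step 2: count simulations.** Assumed: mean 24 control visits, between-person log-rate SD 0.5, one baseline covariate explaining 10-30% of log-rate variance. For N = 80 and 90: rate ratio 1.35, robust SE, 1,000 runs per setting, counts not capped at the 48 target sessions. For N = 86: rate ratio 1.38, dispersion-scaled SE. The imbalance rule was represented by a test between arms at P<0.05. Cells show power when never adjusting / adjusting only if imbalanced / always adjusting.

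| Explained | N = 80 | N = 90 | N = 86 |
|---|---|---|---|
| 10% | 67.3 / 67.3 / 70.0 | 72.7 / 72.9 / 76.0 | 77 / 77 / 80 |
| 20% | 68.3 / 69.7 / 74.9 | 70.0 / 71.0 / 77.8 | 77 / 77 / 83 |
| 30% | 65.0 / 66.0 / 76.3 | 73.6 / 74.5 / 84.2 | 75 / 77 / 88 |

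Gain of always adjusting, in points, in the order N = 80, 90, 86:
- 10%: 2.7, 3.1, 3 over the screen; 2.7, 3.3, 3 over never adjusting.
- 20%: 5.2, 6.8, 6 over the screen; 6.6, 7.8, 6 over never adjusting.
- 30%: 10.3, 9.7, 11 over the screen; 11.3, 10.6, 13 over never adjusting.

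The six values in each row average 17.8/6 = 3.0, 38.4/6 = 6.4 and 65.9/6 = 11.0. In round terms the gain is about 3, 6 to 7, and 10 to 12 points. With 1,000 runs, a power near 70% has a simulation error of √(0.7×0.3/1000) = 1.4 points, so finer distinctions mean little.

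**Step 3: why the screen recovers little.** Under randomisation, a P<0.05 imbalance test admitted the predictive covariate in only about 5-6% of runs. At 30% explained and N = 80, the SD of the estimated log rate ratio was 0.125 never adjusting, 0.121 under the screen and 0.109 always adjusting.

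**Step 4: false positives and the choice of standard error.** With a robust SE and no true effect (N = 80), the screen gave 4.9-5.9% false positives, never adjusting 5.6-6.5% and always adjusting 5.9-6.7%. With the plain Poisson SE, the reported value was 0.046 with or without the covariate, and false positives were 41-51% either way. The precision gain therefore appears in the analysis only if the SE allows for overdispersion.

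**Step 5: cost if the covariates predict nothing.** Age and sex are balanced by the pairing, so the cost comes mainly from the other two terms. The SE factor is about √((N−3)/(N−5)) = √(77/75) = 1.013 at N = 80, and power falls from 80% to Φ(2.802/1.013 − 1.960) = 79%, about 1 point.

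**The case against.** The strongest reply is that nothing in the plan keeps these measures out. The group-difference sentence carries an outcome-relevance condition, the model is multivariable, and the exploration route could admit a balanced predictor. This stands: a reader might infer that the plan excludes baseline activity and motivation, but the text says only that their inclusion is not assured.

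The P<0.05 screen is also an assumption, since the plan gives no entry threshold. In a linear check with 43 per arm, correlation 0.5 and an effect of 0.612 SD, power was 82% with entry at P<0.05, 83% at 0.2 and 86% at 0.5. With entry by association with the outcome it was 89%, the same as fixed adjustment. The power loss therefore depends on how the analyst reads the rule. That leaves the prespecification point untouched.

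The benefit may be small. Main-trial entry requires low recent activity, which narrows the range of step counts; free-living steps are not fitness-center attendance; and the protocol works to remove barriers and supplies transport, which may weaken the link between perceived barriers and visits. All of this is fair and argues for the low end of the range.

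A reader might also infer that choosing covariates by imbalance inflates the type I error. The simulations do not show that. Free choice of covariates after exploration was not simulated, so no figure can be put on it. The high false-positive rate of the plain Poisson SE is a separate matter, arises with or without the covariate, and depends on the assumed overdispersion.

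**Conclusion.** The point holds as one of precision and prespecification. The plan ties covariate choice to observed group differences and open-ended exploration, when baseline measures already being collected could be fixed in the Aim 1 model at almost no cost. It does not show that the primary test is invalid.

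The size of the loss cannot be taken from the documents. Under the P<0.05 screen, log-rate SD 0.5 and an SE that allows for overdispersion, all assumed, it is about 3 points of power at 10% of between-person variance explained, 6 to 7 at 20% and 10 to 12 at 30%. The figure for step count alone may be near 3 points or lower. This is a worthwhile low-cost improvement and not a serious flaw.

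**What to change.** In Data analyses, replace selection by group difference for Aim 1 with a sentence such as:

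> The Aim 1 visit-count model will include randomised group, age, sex, baseline 7-day mean daily steps and one prespecified baseline motivation questionnaire score, all measured before group assignment, regardless of whether the groups differ on them, with a robust or dispersion-scaled standard error.

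Report the model without the steps and motivation terms as a sensitivity analysis.

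Two details must be settled for this to work. The protocol defines no single score from the questionnaire, so one has to be named in advance. It also describes the measures as preceding training without saying when assignment takes place, so their timing before assignment should be confirmed.

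The cost is a few degrees of freedom out of about 80-90 and a simple stated rule for missing baseline values, such as mean imputation. No new data, visits or staff are needed.

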The high-risk youth who will be enrolled in the proposed study live in a predominantly rural, low socioeconomic region of Oklahoma. They currently have access to several well-equipped fitness centers in the region, but these resources are underutilized. Although it is well-accepted that regular exercise can improve individual health and reduce the socioeconomic burden of diabetes, reducing barriers and effectively modifying behavior presents a significant challenge. Prior studies have shown that paying adults for desired behaviors and/or health outcomes can be effective, but the use of financial incentives to shape exercise behavior in adolescents has not been reported. We hypothesize that monetary incentives will encourage obese, insulin resistant American Indian youth to establish and maintain better exercise habits, ultimately resulting in better health. We propose to provide transportation for participants to the wellness centers and individually tailored instruction and oversight by fitness professionals so that the centers are accessible and appealing. The provision of monetary incentives is designed to reinforce the frequency and duration of exercise. Our strategy to accomplish these goals is outlined in the following Specific Aims:

Aim 1: To determine whether financial incentives will increase the frequency of exercise sessions performed by American Indian youth at a community fitness center. Obese, insulin resistant American Indian adolescents will be randomly assigned to one of two groups for a 16-week exercise program: Control (\$4/session, up to 3 sessions/week, provided as compensation for time), or Incentive (\$4, \$10, and \$16 for the first, second, and third session each week, respectively). All participants will be provided transportation to and from the fitness center and professional instruction and supervision for aerobic exercise training, but will differ only in the amount of money they are eligible to collect for their attendance. A secondary goal of this Aim is to assess the association between exercise frequency and changes in diabetes-related risk factors, including insulin sensitivity, body composition, and blood lipids.

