Aim 2: To determine whether financial incentives will increase the duration of exercise performed by American Indian youth at a community fitness center. Participants who complete Aim 1 will be re-randomized to one of two groups for a second 16-week period of exercise: Control (\$4/session, up to 3 sessions/week), or Incentive (\$4, \$7, or \$10 for 20-, 40-, or 60- minute sessions, respectively, up to 3 sessions and \$30/week). Transportation and professional supervision will remain the same as in Aim 1. A secondary goal is to assess the association between exercise duration and changes in diabetes-related risk factors.

Aim 3: To determine whether ongoing incentives are required for maintenance of fitness center utilization established with financial incentives. Participants who complete Aim 2 will enter a third 16-week exercise period with diminished monetary incentives. Each person will be re-randomized to one of two incentive structures: a) Ramp-down, with financial incentives diminishing to zero by 8 weeks, or b) Raffle, with monetary prizes awarded through a drawing in which chances of winning are dependent on frequency and duration of exercise. We hypothesize that exercise behavior will remain above zero even after financial incentives decline and that the Raffle approach will reinforce the best exercise behavior maintenance. Clinical diabetes risk outcomes will be measured as in Aims 1 and 2.

Aim 4: To measure the impact of physical activity and physical fitness on circulating biomarkers of metabolic disease risk. Normal weight American Indian youth with either low physical activity and fitness or high physical activity and fitness will be studied on a single occasion. Serum/plasma concentrations of lipids, amino acids, and related markers of inflammation, and oxidative and vascular stress will be compared among the normal weight participants and the overweight/obese youth enrolled in Aims 1-3.

This study will clarify how specific incentive structures can be used to promote exercise in a population of adolescents at exceptionally high risk for diabetes and cardiometabolic disease. The study will also provide needed insight on the volume of exercise needed to elicit changes in clinical outcomes. These results will be used to develop better lifestyle intervention strategies for American Indian youth.

[figure not shown]
RESEARCH STRATEGY: APPROACH

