Design: Specific Aims 1-3 will follow a single prospective, randomized trial design, with 105 participants

enrolled and 80-90 entering the exercise program (**Fig 1**). The individual Aims are distinguished by sequential study phases and varying incentive structures (**Fig 2 and 3**). Aim 4 is a cross-sectional comparison between overweight/obese participants entering the main trial and two groups of normal weight youth (up to 40 participants per group) with either low physical activity and fitness or high physical activity and fitness (up to 40 participants per group).

Participants: Male and female American Indian youth 11-21 years old will be recruited from the Choctaw Health Service Area of SE Oklahoma. For the primary exercise incentives study, the eligibility criteria include BMI ≥85th percentile for age- and sexspecific norms based on growth charts from the Centers for Disease Control, maturation level ≥Tanner Stage 2 for breasts (girls) or genitalia (boys), family history of T2D, and recent history of low physical activity. Low physical activity, defined as attaining < 30 minutes of structured moderate-to-vigorous intensity exercise on \leq 3 days/week over the preceding 3 months, will be confirmed through guestionnaires and objective monitoring as described below. For both normal weight comparison groups in Aim 4, eligibility will include BMI greater than 20th and less than 85th percentile, maturation level ≥Tanner Stage 2 for breasts (girls) or genitalia (boys), and recent history of either a) low physical activity (same as the overweight/obese group) or, b) high physical activity (>30 minutes of structured moderate-to-vigorous intensity exercise on >3 days/week over the preceding 3 months. T2D family history will be recorded but will not be an inclusion criterion for the normal weight groups. Fitness level and physical activity will be determined through testing, described below. Additional enrollment and retention eligibility criteria are: lack of diabetes or other potentially confounding metabolic disorders, able to safely exercise, willingness to complete the testing and participation schedule, and not on medications known to impact the stated outcomes. A medical history and physical exam will be performed to assure suitability for the study during the initial screening.

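### The covariate rule for the Aim 1 and Aim 2 primary models names weight loss and sets no timing limit, so it permits an adjustment that would dilute the incentive effect

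*Combined protocol and SAP*

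**What the plan says.** The analysis plan is the single Data analyses paragraph of the combined protocol and SAP. After noting that matching on age and sex should make the groups similar at baseline, it plans further comparisons to "identify demographic or other variables on which the groups might differ (e.g., weight loss) that could affect the primary outcomes". The next sentence gives the consequence: "Subsequent analyses will adjust for these potentially confounding variables". The rule is then applied to the main comparison: "Regression models, which adjust for modifier (or confounding) variables identified in initial data exploration, will compare between-group differences in the primary outcomes".

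The Aim 1 outcome is "the number of fitness center visits, which is the primary outcome in Aim 1"; for Aim 2 it is total exercise time. There is no covariate list, no threshold for calling a difference, and no statement of when a covariate must have been measured.

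Three design facts bear on this:

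- Under Specific Aims, Aim 1, the arms "will differ only in the amount of money they are eligible to collect for their attendance".
- Under Baseline pre-training testing, "Baseline tests will be comprised of measurements of daily physical activity, aerobic fitness, body composition, and insulin resistance". Prior weight change is not on that list.
- Under Specific Aims, Aim 2, "Participants who complete Aim 1 will be re-randomized to one of two groups for a second 16-week period of exercise".

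**The concern.** A covariate in a randomised comparison should be fixed before randomisation. Weight loss is a change over time, and in Aim 1 there is no earlier study phase for it to come from. Body mass is measured at the Pre-test and again after the 16 weeks, so the weight loss that the schedule supplies for Aim 1 is measured after the behaviour it would be used to adjust. The plan itself treats change in body composition as something to be related to exercise frequency (secondary goal of Aim 1).

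If the incentive brings more sessions and more sessions bring more weight loss, the arms will tend to differ on weight loss because the incentive worked. The rule would then bring weight loss into the model, and the coefficient for arm would lose part of the effect the trial is meant to estimate. The rule is most likely to act when the incentive has succeeded. With no list or threshold, the reported effect would also depend on which observed differences are acted on.

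**Working it through.** **Inputs from the documents.** The Design section gives "80-90 entering the exercise program", so 40 to 45 per arm in Aim 1; 42 is used. The significance level is 0.05, taken as two-sided because the plan does not say. The documents give no effect size, SD, power or correlation, so there is no stated figure to reproduce.

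**Assumptions.** The true effect is 0.62 SD, chosen because it gives unadjusted power of 0.80 at 42 per arm. The within-arm correlation r between exercise and weight loss ranges from 0.3 to 0.6.

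**Model.** With arm A (0 or 1), exercise S and weight loss W in within-arm SD units:

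- S = τA + e
- W = rS + dA + √(1 − r²)·u

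Here d is any effect of arm on weight that does not pass through counted exercise. The within-arm slope of S on W is r, and the arms differ on W by rτ + d. The adjusted arm coefficient is therefore τ − r(rτ + d) = τ(1 − r²) − rd.

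**Arm affects weight only through counted exercise (d = 0).** Always adjusting gives 0.62 × (1 − r²): 0.62 × 0.91 = 0.564, 0.62 × 0.84 = 0.521, 0.62 × 0.75 = 0.465 and 0.62 × 0.64 = 0.397. Simulation (40,000 trials per cell) agrees and adds power. The trigger columns assume that W enters only when the arms differ on it at p<0.05.

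| r | Always: estimate | Always: power | Trigger: W enters | Trigger: estimate | Trigger: power |
|---|---|---|---|---|---|
| 0.3 | 0.565 | 0.758 | 13.4% | 0.601 | 0.781 |
| 0.4 | 0.520 | 0.717 | 20.0% | 0.575 | 0.752 |
| 0.5 | 0.465 | 0.665 | 29.0% | 0.538 | 0.713 |
| 0.6 | 0.398 | 0.593 | 39.0% | 0.484 | 0.654 |

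Relative to 0.62, shrinkage under the trigger is about 3%, 7%, 13% and 22%. With no true effect, type I error is 0.048 to 0.052 if always adjusted and 0.042 to 0.051 with the trigger. At 40 per arm (unadjusted power 0.78), trigger power for the same r is 0.757, 0.735, 0.693 and 0.637. At 45 per arm (unadjusted 0.83) it is 0.806, 0.787, 0.747 and 0.681.

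**Check with counts.** The plan expects a Poisson model for Aim 1. A separate simulation used overdispersed counts, assumed means of 18 and 24 sessions, 40 per arm and 1,000 trials per scenario. Always adjusting moved the rate ratio from 1.31 to 1.28, 1.22 and 1.15 at r = 0.3, 0.5 and 0.7, and power from about 0.63 to 0.58, 0.47 and 0.35. The pattern is the same.

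**Arm also raises off-site exercise that affects weight (d > 0).** The Exercise training section accepts and logs exercise at home or school, which is not a fitness center visit. With an assumed d = +0.3, always adjusting gives 0.564 − 0.09 = 0.474 at r = 0.3 and 0.465 − 0.15 = 0.315 at r = 0.5. With the trigger, the simulated estimates are 0.510 (power 0.634) and 0.349 (power 0.391).

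**When would the bias be upward?** This needs τ(1 − r²) − rd > τ, that is d < −rτ, which is the same as rτ + d < 0: less weight loss overall in the incentive arm than in control. If paid visits displaced off-site exercise one for one, d = −rτ and the adjusted coefficient is τ(1 − r²) + r²τ = τ, with no bias.

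**The case against.** The strongest reply is that the sentence describes ordinary baseline checks: it follows a remark about baseline similarity, admits only variables that could affect the outcome, and calls them potential confounders. Weight loss caused by the counted exercise is not a confounder, so a careful analyst could exclude it under the rule's own terms. This narrows the point to what the rule permits. It does not remove it, because weight loss is not a listed baseline measure, it is the only example given, and no sentence excludes change within the phase. A medical history might supply an earlier weight change, but the plan does not say that this is meant.

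For Aim 2 the reply is partly right: weight change during Aim 1 precedes the new randomisation and is a legitimate covariate.

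It can also be said that the correlation may be weak. The study sets no weight-loss goals and does not monitor diet, and participants are 11 to 21 years old, many perhaps still growing. That is fair, and at r of 0.3 or below the loss is small.

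A reader might infer more: that the rule could create false positives or exaggerate the incentive effect. The documents do not support this. Upward bias needs the incentive arm to lose less weight overall, and nothing in the plan suggests it. Inflated type I error needs the incentive to shift weight while adding no counted exercise, for example by raising unpaid off-site activity without raising paid visits. No such mechanism is described. The plan also says that logged extra activity may be used in the analysis where applicable; this is vague, but the off-site route is not ignored.

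**Conclusion.** The concern holds as a defect in the covariate rule. As written, it allows the Aim 1 and Aim 2 primary comparisons to be adjusted for weight loss in the same phase, and in Aim 1 that is the only weight loss the test schedule yields. It would be too strong to say that the plan commits to this adjustment or that bias is certain.

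The expected harm is attenuation and lost power, with type I error at or below about 0.05 when arm affects weight only through counted exercise. Under the assumptions above, the loss becomes material from r of about 0.4, or at lower r if the incentive also raises off-site exercise that affects weight. Upward bias and inflated type I error remain theoretical possibilities. The wording problem is clear from the text; its size rests wholly on assumed values of r, the effect and the trigger. The figures apply to the numbers entering Aim 1; Aim 2 may have fewer participants.

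**What to change.** In the Data analyses section:

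1. Delete weight loss as the example.
2. Replace selection by observed group difference, for the primary models, with a short covariate list fixed in advance and restricted to variables measured before the randomisation of the phase being analysed. It should hold at least the matching factors, age and sex. For Aim 2 it may include weight change during Aim 1.
3. Report any model that adjusts for same-phase weight change, or for another variable arising after randomisation, only as a labelled exploratory analysis.

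The cost is a change of analysis wording and a few model degrees of freedom. No new data are needed.
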